5.2.1.2. F/R/TAF, Odefsey[®]

F/R/TAF tablets are capsule-shaped, film-coated gray tablets debossed with "GSI" on one side and "255" on the other side. Each F/R/TAF tablet contains 200 mg of FTC, 25 mg of RPV (as 27.5 mg RPV hydrochloride), and 25 mg of TAF (as 28 mg of TAF fumarate).

In addition to the active ingredients, the tablets contain lactose monohydrate, microcrystalline cellulose, polysorbate, povidone, croscarmellose sodium and magnesium stearate. The tablet cores are film-coated with polyvinyl alcohol, titanium dioxide, polyethylene glycol, talc, and black iron oxide.

5.2.1.3. LDV/SOF, Harvoni[®]

LDV/SOF tablets are orange, diamond-shaped, film-coated tablets debossed with "GSI" on one side and "7985" on the other side. Each LDV/SOF FDC tablet contains 90 mg of LDV and 400 mg of SOF.

In addition to the active ingredients, the tablets contain lactose monohydrate, copovidone, microcrystalline cellulose, croscarmellose sodium, colloidal silicon dioxide, magnesium stearate, polyvinyl alcohol, titanium dioxide, talc, polyethylene glycol, and FD&C yellow # 6 /sunset yellow FCF aluminium lake.

5.2.2. Packaging and Labeling

Study drug(s) to be distributed to centers in the US and other participating countries shall be labeled to meet applicable requirements of the United States Food and Drug Administration (FDA) and/or other local regulations.

5.2.2.1. E/C/F/TAF, Genvoya[®]

E/C/F/TAF tablets are packaged in white, high density polyethylene (HDPE) bottles. Each bottle contains 30 tablets, silica gel desiccant, and polyester packing material. Each bottle is enclosed with a white, continuous thread, child-resistant polypropylene screw cap with an induction-sealed, and aluminum-faced liner. Commercially available product of Genvoya[®] may also be used for the study.

5.2.2.2. F/R/TAF, Odefsey[®]

F/R/TAF tablets are packaged in white, high density polyethylene (HDPE) bottles. Each bottle contains 30 tablets, silica gel desiccant, and polyester packing material. Each bottle is enclosed with a white, continuous thread, child-resistant polypropylene screw cap with an induction-sealed, and aluminum-faced liner. Commercially available product of Odefsey[®] may also be used for the study.

5.2.2.3. LDV/SOF, Harvoni[®]

LDV/SOF tablets are packaged in white, high density polyethylene (HDPE) bottles. Each bottle contains 28 or 30 tablets, silica gel desiccant and polyester packing material. Each bottle is enclosed with a white, continuous thread, child-resistant polypropylene screw cap with an induction-sealed, and aluminum-faced liner. Commercially available product of Harvoni[®] may also be used for the study.

5.2.3. Storage and Handling

E/C/F/TAF, F/R/TAF, and LDV/SOF tablets should be stored at controlled room temperature of 25 °C (77 °F); excursions are permitted between 15 °C and 30 °C (59 °F and 86 °F). Storage conditions are specified on the label. Until dispensed to the subjects, all bottles of study drug should be stored in a securely locked area, accessible only to authorized site personnel.

To ensure the stability and proper identification, study drugs should not be stored in a container other than the container in which they were supplied. Consideration should be given to handling, preparation, and disposal through measures that minimize drug contact with the body. Appropriate precautions should be followed by avoiding direct eye contact or exposure when handling.

Commercial product of Genvoya[®], Odefsey[®], and Harvoni[®] may be used for the study. Further information regarding storage and handling are available in the Prescribing Information for commercial products.

5.3. Dosage and Administration of E/C/F/TAF, F/R/TAF, and LDV/SOF

E/C/F/TAF FDC, F/R/TAF FDC, and LDV/SOF FDC tablets will be provided by Gilead Sciences.

The two HIV study treatments will be administered orally, once daily with food at approximately the same time each day:

- Elvitegravir 150 mg/cobicistat 150 mg/emtricitabine 200 mg/tenofovir alafenamide 10 mg (E/C/F/TAF) FDC
- Emtricitabine 200 mg/rilpivirine 25 mg/tenofovir alafenamide 25 mg (F/R/TAF) FDC

HCV study treatment (ledipasvir 90 mg/sofosbuvir 400 mg [LDV/SOF] FDC) is to be administered orally, once daily with or without food at approximately the same time each day.

For a missed dose of E/C/F/TAF FDC, F/R/TAF FDC, and/or LDV/SOF FDC tablet, subjects should be instructed to take the missed dose of study drug as soon as possible during the same day. Subjects should be cautioned never to double the next dose with a missed dose of study drug under any circumstances.

5.4. Prior and Concomitant Medications

The use of medications for the treatment of HIV and HCV, other than the study treatments (ie, E/C/F/TAF, F/R/TAF, or LDV/SOF), is prohibited.

Should subjects have a need to initiate treatment with any excluded concomitant medication, the Gilead Medical Monitor must be consulted prior to initiation of the new medication. In instances where an excluded medication is initiated prior to discussion with the Medical Monitor, the Investigator must notify Gilead as soon as he/she is aware of the use of the excluded medication.

Concomitant medications taken within 30 days prior to the Screening visit and up to and including 30 days after the last dose of study drug need to be recorded in the source documents and electronic case report form(s) (eCRFs).

Medications listed in Table 5-1 (E/C/F/TAF + LDV/SOF) and Table 5-2 (F/R/TAF + LDV/SOF) and use of herbal/natural supplements are excluded or should be used with caution while subjects are participating in the study due to potential drug-drug interactions.

Drug Class	Agents Disallowed	Use With Caution	
Acid Reducing Agents Antacids ^a		Elvitegravir plasma concentrations are lower with antacids due to local complexation in the GI tract and not to changes in gastric pH. It is recommended to separate study drug and antacid administration by at least 2 hours.	
		Proton-Pump Inhibitors, H2-Receptor Antagonists, Antacids	
Alpha Adrenergic Receptor Antagonists	Alfuzosin		
Analgesics		Tramadol, Propoxyphene: Concentrations may increase with study drug(s); clinical monitoring is recommended.	
Antiarrhythmics	Amiodarone ^c , Quinadine	Flecainide Quinidine, Propafenone, Systemic Lidocaine, Mexiletine, Disopyramide: Concentrations may increase with study drug(s) resulting in a potential for cardiac arrhythmias; clinical and ECG monitoring is recommended.	
		Concentrations of clarithromycin and/or cobicistat may be altered when clarithromycin is coadministered with study drug(s).	
Antibacterials		Patients with CL_{cr} greater than or equal to 60 mL/min: No dose adjustment of clarithromycin is required.	
		Patients with CL_{cr} between 30 mL/min and 60 mL/min: The dose of clarithromycin should be reduced by 50%.	
		Concentrations of telithromycin and/or cobicistat may be increased when telithromycis in coadministered with study drug. Clinical monitoring is recommended upon coadministration with study drug.	
Anticoagulants		Warfarin: Concentrations may increase or decrease with study drug(s); appropriate INR (International Normalized Ratio) monitoring is recommended.	
Anticonvulsants ^b	Phenobarbital, Phenytoin, Carbamazepine, Oxcarbazepine	Ethosuximide, Divalproex, Lamotrigine: Concentrations may increase with study drug(s); clinical monitoring is recommended.	

Table 5-1.	Prior and Concomitant Med	lications – E/C/F/TAF + LDV/SOF

Drug Class	Agents Disallowed	Use With Caution	
		Selective serotonin reuptake inhibitors (SSRIs): A dose reduction may be required for most drugs of this class with the exception of sertraline.	
Antidepressants		Tricyclics: Concentrations may increase or decrease with study drug(s). Concentration monitoring is recommended to ensure adequate clinical response.	
		Trazodone: Concomitant use with CYP3A inhibitors results in increased concentrations and adverse events; dose reduction should be considered.	
Antifungals		Ketoconazole and Itraconazole: Concomitant use with study drug may result in an increase in concentrations. Daily dose of ketoconazole and itraconazole should be restricted to 200 mg. Subjects receiving ketoconazole or itraconazole should be monitored for adequate clinical response.	
		Voriconazole: Concomitant use with study drug may result in an increase in concentrations. Clinical monitoring may be needed.	
Antigout		Dose reductions of colchicine may be required. Study drug(s) should not be coadministered with colchicine in patients with renal or hepatic impairment.	
Antihistamines		Concentrations of astemizole and terfenadine may be increased when coadministered with cobicistat. Clinical monitoring is recommended when these agents are coadministered with study drug(s).	
Antimycobacterials ^b	Rifampin, Rifapentine, Rifabutin		
β-Blockers		Metoprolol, Timolol: Clinical and ECG monitoring of subjects is recommended. A dose decrease may be needed.	
Calcium Channel Blockers	Bepridil	Felodipine, Nifedipine, Nicardipine, Verapamil, Diltiazem, Amlodipine: Concentrations may increase with study drug(s). Clinical and ECG monitoring of subjects is recommended	
Cardiac Medications		Digoxin ^d	
Corticosteroids: Inhaled/Nasal		Concomitant use of inhaled fluticasone and study drug(s) may increase plasma concentrations of fluticasone. Use is not recommended unless the potential benefit to the subject outweighs the risks of corticosteroid side effects. Alternatives should be considered, particularly for long-term use.	

Drug Class	Agents Disallowed	Use With Caution
Corticosteroids: Systemic		Systemic dexamethasone, a CYP3A inducer, may significantly decrease elvitegravir and cobicistat plasma concentrations, which may result in loss of therapeutic effect and development of resistance. Alternative corticosteroids should be considered.
		Use of Prednisone as a steroid burst (≤ 1 week of use) should be monitored appropriately.
Endothelin Receptor Antagonists		Bosentan: Coadministration may lead to decreased elvitegravir exposures and loss of therapeutic effect and development of resistance. Alternative endothelin receptor antagonists may be considered.
Ergot Derivatives	Ergotamine, Ergonovine Dihydroergotamine Methylergonovine Ergometrine	
GI Motility Agents	Cisapride	
Herbal/Natural Supplements ^b	St. John's Wort, Echinacea, Milk thistle (ie, silymarin), Chinese herb sho-saiko-to (or Xiao-Shai-Hu-Tang)	
HMG-CoA Reductase Inhibitors	Simvastatin, Lovastatin, Rosuvastatin ^e	Atorvastatin: Concentrations may increase with study drug(s). Start with the lowest dose; gradual increase in dose may be tailored to clinical response. Careful monitoring for signs and symptoms of muscle weakness or myopathy, including rhabdomyolysis.
Immunosuppressants		Cyclosporine, Rapamycin, Sirolimus, Tacrolimus: Concentrations may increase with study drug(s). Therapeutic monitoring should be considered.
Inhaled Beta Agonist	Salmeterol	
Neuroleptics	Pimozide	Perphenazine, Risperidone, Thioridazine: A dose decrease may be needed.

Drug Class	Agents Disallowed	Use With Caution	
		Methadone: Methadone exposures are unaffected upon coadministration with elvitegravir and cobicistat. No dose adjustment of methadone is required upon coadministration with study drug(s).	
		Meperidine (Pethidine): Dosage increase and long-term use are not recommended due to increased levels of metabolite normeperidine, which has analgesic and CNS stimulant (eg, seizures) activities.	
Opiates		Buprenorphine: Concentrations of buprenorphine and norbuprenorphine are modestly increased and concentrations of naloxone are modestly decreased when coadministered with elvitegravir and cobicistat, with no effect on opioid pharmacodynimcs. The concentration changes are not considered clinically relevant and no dose adjustment of buprenorphine/naloxone is required upon coadministration with study drug(s).	
		Pulmonary Arterial Hypertension:	
Phosphodiesterase-5 Inhibitors	Sildenafil (for PAH)	Tadalafil: Caution should be exercised, including consideration of dose reduction, when coadministered for treatment of pulmonary arterial hypertension.	
		Erectile Dysfunction:	
		Sildenafil, Vardenafil, Tadalafil: It is recommended that a single dose of Sildenafil no more than 25 mg in 48 hours, Vardenafil no more than 2.5 mg in 72 hours, or Tadalafil no more than 10 mg in 72 hours be coadministered.	
Sedatives/Hypnotics	Orally administered Midazolam, Triazolam	Buspirone, Clorazepate, Diazepam, Estazolam, Flurazepam, Zolpidem: A dose decrease may be needed for these drugs. Clinical monitoring is recommended.	

a It is recommended to separate antacid and LDV/SOF administration by 4 hours. H2-receptor antagonists may be administered simultaneously with or staggered from LDV/SOF at a dose that does not exceed doses comparable to famotidine 40 mg twice daily. Proton-pump inhibitor doses comparable to omeprazole 20 mg can be administered simultaneously with study drugs. Proton-pump inhibitors should not be taken before study drugs.

b May result in a decrease in the concentrations of study drugs.

c May result in symptomatic bradycardia. Mechanism is currently unknown. The use of amiodarone is prohibited from 60 days prior to Day 1 through the end of treatment

e Use with study drug may result in an increase in the concentration of rosuvastatin, which is associated with increased risk of myopathy including rhabdomyolysis

d Coadministration of E/C/F/TAF or LDV/SOF with digoxin may increase the concentration of digoxin. Caution is warranted and therapeutic concentration monitoring of digoxin is recommended when coadministered with E/C/F/TAF or LDV/SOF.

Drug Class	Agents Disallowed	Use With Caution
Acid Reducing Agents ^a	Proton pump inhibitors, such as Esomeprazole, Lansoprazole, Omeprazole, Pantoprazole, Rabeprazole	H2-Receptor Antagonists, Antacids Cimetidine, Famotidine, Nizatidine, Ranitidine Coadministration of H2-receptor antagonists (H2RA) may cause significant decreases in RPV plasma concentrations (increase in gastric pH). H2RAs should only be administered at least 12 hours before or at least 4 hours after F/R/TAF
Alkaline antacids: antacids (eg, aluminum or magnesium hydroxide, calcium carbonate)		Antacids should be used with caution as coadministration may cause significant decreases in RPV plasma concentrations (increase in gastric pH). Antacids should only be administered either at least 2 hours before or at least 4 hours after F/R/TAF.
Antiarrhythmics	Amiodarone ^c , Quinidine	
Anticonvulsants ^b	Carbamazepine, Oxcarbazepine, Phenobarbital, Phenytoin	
Antifungals		Fluconazole, Itraconazole, Ketoconazole, Posaconazole, Voriconazole: may increase concentration of RPV.
Antimycobacterials ^b	Rifapentine, Rifabutin, Rifampin	
Cardiac Medications		Digoxin ^d
Corticosteroids: Systemic	Dexamethasone (more than a single dose)	
Herbal/Natural Supplements ^b	St. John's Wort, Echinacea, Milk thistle (ie, silymarin), Chinese herb Sho-Saiko-To (or Xiao-Shai-Hu-Tang)	
HMG-CoA Reductase Inhibitors ^e	Rosuvastatin	
Narcotic analgesics		Methadone Clinical monitoring is recommended as methadone maintenance therapy may need to be adjusted in some patients upon coadministration with RPV

	Table 5-2.	Prior and Concomitant Medications – F/R/TAF + LDV/SOF
--	------------	---

a It is recommended to separate antacid and LDV/SOF administration by 4 hours. H2-receptor antagonists may be administered simultaneously with or staggered from LDV/SOF at a dose that does not exceed doses comparable to famotidine 40 mg twice daily. Proton-pump inhibitor doses comparable to omeprazole 20 mg can be administered simultaneously with study drugs. Proton-pump inhibitors should not be taken before study drugs.

b May result in a decrease in the concentrations of study drugs.

c May result in symptomatic bradycardia. Mechanism is currently unknown. The use of amiodarone is prohibited from 60 days prior to Day 1 through the end of treatment

d Coadministration of F/R/TAF or LDV/SOF with digoxin may increase the concentration of digoxin. Caution is warranted and therapeutic concentration monitoring of digoxin is recommended when co-administered with F/R/TAF or LDV/SOF.

e Use with study drug may result in an increase in the concentration of rosuvastatin, which is associated with increased risk of myopathy including rhabdomyolysis.

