3.4. Duration of Treatment

The HIV treatment duration is from the Day 1 visit until the last study visit at the Post-HCV Treatment Week 12. The HCV treatment duration is 12 weeks. Screening assessments will be completed within 42 days of the Day 1 visit.

All subjects will complete the following study visits: Screening, Day 1, Weeks 4, 6 (laboratory visit only), 8 (start of HCV treatment), 12, 16, and 20 (end of HCV treatment), and post-HCV treatment visits 4 and 12 weeks after the last LDV/SOF dose.

Subjects who complete the study through the last study visit at the Post-HCV Treatment Week 12 visit will be required to return to the clinic 30 days after the completion of the study treatment for a 30-Day Follow-Up visit.

- a Following the Day 1 visit, subjects will return for study visits at Weeks 4, 6 (laboratory visit only), 8, 12, 16, 20, and Post-HCV Treatment 4 and 12 weeks after the last LDV/SOF dose.
- b Part 1: subjects are randomized to either E/C/F/TAF FDC or F/R/TAF FDC on Day 1 and maintain HIV treatment to the Week 8 visit.
- c Part 2: At Week 8, once HIV-1 RNA suppression (< 50 copies/mL) is confirmed (based on the Week 6 HIV-1 RNA value), subjects will start on LDV/SOF FDC for 12 weeks (until Week 20) while maintaining their HIV treatment. At Week 20, LDV/SOF FDC will be discontinued while continuing HIV treatment. Subjects will continue in the study for another 12 weeks to determine SVR4 (4 weeks post-HCV treatment) and SVR12 (12 weeks post-HCV treatment).

- d Subjects who complete the study through the Post-HCV Treatment Week 12 visit will be required to return to the clinic 30 days after the completion of the study treatment for a 30-Day Follow-Up Visit.
- e At the Day 1 visit, subjects will switch to either E/C/F/TAF FDC or F/R/TAF FDC and continue on HIV treatment until the last study visit at the Post-HCV Treatment Week 12 visit.

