6.4.2. HIV Treatment and Post-HCV Treatment Assessments (Post-HCV Treatment Weeks 4 and 12)

The following evaluations are to be completed at the end of 4 and 12 weeks after completion of HCV treatment (Post-HCV Treatment Weeks 4 and 12 visits, respectively) and should be timed from the date of last administration of the HCV treatment. The Post-HCV Treatment Week 4 visit is to be completed \pm 2 days, and the Post-HCV Treatment Week 12 visit is to be completed within \pm 4 days; however, unless notified by Gilead Sciences, the Post-HCV Treatment Week 4 and 12 should be completed within 2 and 4 days of the protocol-specified visit date, respectively.

All subjects must complete the Post-HCV Treatment Weeks 4 and 12 visits. The end of study will occur at the Post-HCV Treatment Week 12 visit.

The following assessments are to be completed:

- Review AEs and changes in concomitant medications
- Complete physical examination (**Post-HCV Treatment Week 12 only**) (urogenital/anorectal exams will be performed at the discretion of the Investigator)
- Perform symptom-directed physical examination as needed
- Obtain vital signs, including weight
- Obtain urine samples for the following laboratory analyses:
 - Urinalysis and urine chemistry
 - Urine pregnancy test (females of childbearing potential only); positive urine pregnancy tests will be confirmed with a serum test. If the serum test is positive, the subject will be discontinued.
 - Renal tubular function assessments (Post-HCV Treatment Week 12 only)
 - Urine sample storage for possible additional clinical testing
- Obtain blood samples for the following laboratory analyses:
 - Chemistry profile
 - Hematology profile
 - Coagulation assessments
 - Metabolic assessments (Post-HCV Treatment Week 12 only)

- CD4+ cell count
- Plasma HIV-1 RNA
- Plasma HCV RNA
- Serum bone safety assessments (Post-HCV Treatment Week 12 only)
- Platelet and coagulation function assessments (Post-HCV Treatment Week 12 only)
- Inflammation assessments (Post-HCV Treatment Week 12 only)
- Plasma storage samples for virology, safety, and/or PK testing
- Serum storage sample for possible additional clinical testing

- PPD

- Obtain estimated glomerular filtration rate according to the Cockcroft-Gault formula (see Section 4.2 for details)
- Complete questionnaires (Post-HCV Treatment Week 12 only): subject is to read questionnaire by her/himself and write/mark answers directly onto the questionnaires.
 - VAS for HIV adherence

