6.5. Post-treatment Assessments

6.5.1. Early Study Drug Discontinuation (ESDD) Visit

Early study drug discontinuation during Part 1 (Day 1 through Week 8):

If the subject discontinues HIV study drug dosing in Part 1, the subject will be discontinued from the study and will not continue to Part 2 of the study. The subject will be asked to return to the clinic within 72 hours of stopping HIV study drugs for the ESDD visit, followed by the 30-Day Follow-Up visit.

Early study drug discontinuation during Part 2 (after initiation of HCV treatment):

If the subject discontinues HCV study drug dosing only prior to completing the 12-week HCV treatment, the following will occur:

- Be asked to return to the clinic within 72 hours of stopping HCV study drug for the ESDD visit.
- Remain in the study to return for follow-up visits 4 and 12 weeks after the last dose of LDV/SOF, as described in Section 6.4.2.
- Continue to receive HIV study drugs (see ESDD procedures below).

If the subject discontinues HIV study drug dosing only, the following will occur:

- Be asked to return to the clinic within 72 hours of stopping HIV study drugs for the ESDD visit.
- HIV regimen may be changed, after discussion with the Medical Monitor. The new HIV regimen should be designed to allow continued dosing of LDV/SOF. LDV/SOF should be continued unless an HIV regimen cannot be constructed that would allow coadministration with the new HIV regimen.
- Remain in the study to complete the 12-week HCV treatment (see Section 6.4.1) and follow-up visits 4 and 12 weeks after the last dose of LDV/SOF, as described in Section 6.4.2.

If the subject discontinues both HIV and HCV study drug dosing, the following will occur:

- Be asked to return to the clinic within 72 hours of stopping study drugs for the ESDD visit.
- Remain in the study to return for follow-up visits 4 and 12 weeks after the last dose of LDV/SOF, as described in Section 6.4.2.

At the ESDD Visit, any evaluations showing abnormal results indicating that there is a possible or probable causal relationship with the study drugs, should be repeated weekly (or as often as deemed prudent by the Investigator) until the abnormality is resolved, returns to baseline, or is otherwise explained.

The following evaluations are to be completed at the ESDD Visit:

- Review of AEs and changes in concomitant medications

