- Upon confirmation of HIV-1 RNA ≥ 50 copies/mL, potential causes of virologic failure should be documented. Assessment should include:

- Adherence

- Concomitant medication
- Comorbidities (eg, active substance abuse, depression, other intercurrent illnesses)
- All subjects with confirmed virologic failure should be discussed with the Medical Monitor.
- If virologic rebound is confirmed at the scheduled or unscheduled visit and the HIV-1 RNA value is ≥ 400 copies/mL, the blood samples from that visit will be used for HIV-1 genotype/phenotype testing.
- If genotypic/phenotypic resistance to study drug is documented, HIV study drugs (E/C/F/TAF or F/R/TAF) should be discontinued.
- If the HIV study drugs (E/C/F/TAF or F/R/TAF) are discontinued, a new HIV regimen should be constructed, after discussion with the Medical Monitor. The new HIV regimen should be designed to allow continued dosing of LDV/SOF. LDV/SOF should be continued unless an HIV regimen cannot be constructed that would allow coadministration with the new HIV regimen.

If no resistance is detected from genotype/phenotype testing, the subject may remain on HIV study drugs and an HIV-1 RNA should be repeated (2 to 4 weeks after date of test with viral load \geq 50 copies/mL). Investigators should carefully evaluate the benefits and risks of remaining on HIV study drug for each individual subject and document this assessment in the source documents. Investigators who opt to discontinue HIV study drugs for an individual subject must discuss with the Medical Monitor prior to study drug discontinuation.

Please refer to Figure 6-1 for the management of subjects who meet the criteria for virologic rebound.

Figure 6-1. HIV Virologic Rebound Schema

- a If virologic rebound is not confirmed, the subject will remain on their current HIV regimen.
- b If virologic rebound is confirmed, and the HIV-1 RNA is \geq 400 copies/mL, the HIV-1 genotype and phenotype (reverse transcriptase, integrase, and protease) will be analyzed.
- c Based on the results of the genotype/phenotype assays, the subject will remain on HIV study drugs or study drugs will be discontinued. If genotyping/phenotyping fails, a new ARV regimen may be configured at the discretion of the Investigator.
- d If no resistance detected, HIV-1 RNA will be repeated (2 to 4 weeks later). Investigator reviews HIV study drug continuation/discontinuation options and discuss with Medical Monitor prior to study drug discontinuation.

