6.11. End of Study

End of study is defined as completion of the Post-HCV Treatment Week 12 visit and the 30-Day Follow-Up visit.

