- p Plasma storage samples for safety, virology, and/or PK testing. Serum storage samples for possible additional clinical testing.

q PPD

- r Estimated GFR according to the Cockcroft-Gault formula for creatinine clearance (see Section 4.2 for details)
- s Two (2) blood samples will be collected: 1) the predose sample should be drawn prior to observed study drug dosing; 2) the postdose sample should be drawn between 15 mins and 4 hours postdose
- t Health related questionnaires: adherence for HIV (VAS), HIVTSQs Status version (at Day 1 only), HIVTSQc Change version (at all other visits), SF-36, FACIT-F, CLDQ-HCV, and WPAI: Hepatitis C.
- Part 1: HIV study drugs are dispensed after all Day 1 assessments are completed and randomization occurred, and through the duration of the study.
 Part 2: After determination of HIV suppression (< 50 copies/mL) based on the Week 6 HIV-1 RNA value and tolerability of HIV study drugs, LDV/SOF will be dispensed at Weeks 8, 12, and 16 only.

Post-HCV Treatment Week 12: drug accountability only; study drug will not be dispensed at this visit.

v If subjects discontinue during Part 1, only drug accountability will be performed; study drug will not be dispensed at this visit. In Part 2, if subject discontinues LDV/SOF but still continues with HIV study drug, HIV study drug will be dispensed until the last study visit. If subject discontinues HIV study drug but still continues with LDV/SOF, LDV/SOF will be dispensed. If subject discontinues both HIV and HCV study drugs, only drug accountability will be performed; no dispensation will occur at this visit.

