3.1.2. Efficacy Analysis Sets

For this HIV/HCV-coinfection study, the data will be analyzed to assess the treatment efficacy to both HIV and HCV. Therefore, efficacy analysis sets will be defined separately for the HIV drugs, E/C/F/TAF and F/R/TAF, and the HCV drug, LDV/SOF.

HIV Full Analysis Set

The HIV Full Analysis Set (HIV FAS) will include all subjects who (1) are randomized into the study and (2) have received at least 1 dose of HIV study drug, E/C/F/TAF or F/R/TAF. Subjects will be grouped according to the treatment to which they were assigned at randomization. For the HIV FAS, all efficacy data, including data collected after the last dose of HIV study drug, will be included, unless specified otherwise. This is the primary analysis set for the efficacy analyses of HIV study drug.

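### SAP Week 32 HIV-1 RNA: an open-ended window and a latest-record rule put the off-study-drug 30-Day Follow-Up sample in the tertiary suppression tables, and the protocol passages covering that period need reconciling

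*Protocol*

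**What the plan says.** **When study HIV drug ends.** Protocol 3.4: "The HIV treatment duration is from the Day 1 visit until the last study visit at the Post-HCV Treatment Week 12". For that visit, Appendix 2 footnote u specifies "drug accountability only; study drug will not be dispensed at this visit".

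**What is measured afterwards.** Protocol 6.5.2 brings completers back about 30 days later, with a window of 6 days either way, and plasma HIV-1 RNA is among the samples. SAP 2.2 holds the final analysis until that visit is done, so the result will be in the database.

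**How the SAP assigns it.**
- Table 3-1 gives Week 32 a nominal day of 224 and a window of Day 197 or later, with no upper limit. Section 3.8.2.1 explains that Week 32 is its name for Post-HCV Treatment Week 12.
- Section 3.8.3 selects the latest HIV-1 RNA record in a window.
- Section 3.1.2, on the HIV FAS: "all efficacy data, including data collected after the last dose of HIV study drug, will be included, unless specified otherwise".
- Section 6.3.2.6 tabulates HIV-1 RNA below 50 copies/mL at all visits under missing=failure (M=F) and missing=excluded (M=E), with between-arm differences and exact 95% CIs. It states no on-treatment limit. Neither does Section 3.6.1.3 or Appendix 4 item 11, which deal with the same tables.

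**What the protocol says about the same period.** Section 5.4: "The use of medications for the treatment of HIV and HCV, other than the study treatments (ie, E/C/F/TAF, F/R/TAF, or LDV/SOF), is prohibited". Section 6.5.1, for subjects who stop HIV study drug in Part 2: "HIV regimen may be changed, after discussion with the Medical Monitor". Section 6.9.1, where HIV study drug is stopped after rebound: "a new HIV regimen should be constructed, after discussion with the Medical Monitor". On when the study ends, Section 6.4.2 says "The end of study will occur at the Post-HCV Treatment Week 12 visit" and Section 6.11 says "End of study is defined as completion of the Post-HCV Treatment Week 12 visit and the 30-Day Follow-Up visit".

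**The concern.** A table headed Week 32 is meant to show suppression at the end of randomized HIV treatment. Under the rules as written, a completer's scheduled on-drug sample is displaced by one taken about a month after study drug stopped. That later value may reflect a non-study regimen, no regimen or commercial supply of the same drug, and the table would not say which. The estimated proportions and arm differences would then not describe E/C/F/TAF or F/R/TAF.

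The SAP already has the tool to prevent this. Section 6 defines on-HIV-treatment data as running to the last dose of HIV study drug plus 1 day. The snapshot analysis (6.2.2.2) and the observed CD4 analysis (6.3.2.7) both use that limit. Its absence from 6.3.2.6 looks like an omission.

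The secondary issue is for sites. The Section 5.4 prohibition gives no period and does not refer to the sections that provide for replacement regimens. Because 6.4.2 and 6.11 close the study at different visits, a site cannot tell whether a non-study antiretroviral taken between those visits is a protocol deviation.

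**Working it through.** **1. Reproduce the SAP's own figures.**
- Post-HCV Treatment Week 12 = (8 + 12 + 12) weeks × 7 = Day 224, as in Table 3-1.
- Lower bound of Week 32: the midpoint of the Week 24 and Week 32 nominal days is (168 + 224) / 2 = 196, so the window starts on Day 197, as in Table 3-1.

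**2. Place the 30-Day Follow-Up.** The inputs are the ±4 day window at Post-HCV Treatment Week 12 (Protocol 6.4.2), the 30 ± 6 days to follow-up (6.5.2), and the possible 2 to 4 week delay in starting LDV/SOF after an unconfirmed Week 6 value of 50 copies/mL or more (6.9.1).

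| Delay to LDV/SOF start | Post-HCV Week 12 sample | 30-Day Follow-Up sample |
|---|---|---|
| None | 224 ± 4 = Day 220–228 | 220 + 24 to 228 + 36 = Day 244–264 |
| 2 weeks | 238 ± 4 = Day 234–242 | 234 + 24 to 242 + 36 = Day 258–278 |
| 4 weeks | 252 ± 4 = Day 248–256 | 248 + 24 to 256 + 36 = Day 272–292 |

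**3. Apply the SAP rules to a completer with both samples.**
- Both samples fall on or after Day 197, so both are in the Week 32 window.
- The follow-up sample is 24 to 36 days later, so the latest-record rule selects it.
- With the last dose taken at the Post-HCV Week 12 visit, the on-HIV-treatment limit would be one day later (nominally Day 225). The follow-up sample is beyond that limit in every row.
- Section 6.3.2.6 does not apply the limit, so the off-study-drug value is the one tabulated.

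**4. Check which analyses are reached.**
- Secondary HIV endpoint: the snapshot window is Days 155–196, on-treatment only. The earliest follow-up day for a completer is 244, so it is not reached.
- Observed CD4 summaries: confined to on-HIV-treatment data, so not reached.
- Primary SVR12: based on HCV RNA with its own windows, so not reached by this HIV-1 RNA rule.
- M=F and M=E tables at Week 32, with their arm differences and CIs: reached.

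**5. Size.** The documents give no basis for predicting how many follow-up values would differ in category from the on-drug value, so the effect on the estimate is unknown in size and direction. With 60 planned per arm, each reclassified subject moves that arm's M=F proportion by 1/60 = 1.7 percentage points. M=E moves by at least as much, since its denominator cannot be larger. The number affected runs from none to all completers.

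**The case against.** The strongest reply is about reach. These are tertiary tables, and the endpoints that carry the trial's conclusions are untouched. That stands, and it limits the weight of the point.

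A second reply is that keeping data after the last dose is a deliberate HIV FAS choice, in the spirit of treatment policy. That is reasonable for early discontinuers. It does not explain this result, because completers stop study drug by design and Week 32 is the SAP's own label for the visit at which they stop.

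A third is that the tertiary endpoint definitions might restrict the data. The body of SAP 6.3.1 does not appear in the text available for this review, so such a restriction cannot be ruled out.

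On the protocol, a reader might infer something stronger: that Section 5.4 admits no exception, leaving completers with no permitted antiretroviral and so untreated for a month. The documents do not support that:
- Section 5.4 exempts E/C/F/TAF and F/R/TAF by drug name. Its next paragraph sets out a Medical Monitor consultation step for excluded medicines, though it does not say that consultation amounts to permission.
- Sections 6.5.1 and 6.9.1 provide for replacement regimens.
- The prohibition cannot be unlimited in time, since subjects must be on another antiretroviral regimen at screening.
- Sections 6.4.2 and 6.5.2 place the 30-Day visit after the study is complete, and 6.12 then leaves care with the treating physician. Only 6.11 counts that visit as part of the study.
- SAP 7.4.1 expects non-study antiretrovirals during or after the study.

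The follow-up sample is therefore established only as off study drug, not as off treatment.

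**Conclusion.** The SAP point holds. As written, the Week 32 HIV-1 RNA result in the M=F and M=E tables is the 30-Day Follow-Up sample for every completer who has both samples, at most about 120 subjects. The consequence is confined to those tertiary tables and their between-arm differences. It should be corrected before the final analysis, but it does not threaten SVR12 or the Week 24 snapshot.

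This rests on two assumptions: that completers take their last study HIV dose at about the Post-HCV Treatment Week 12 visit, as Protocol 3.4 and Appendix 2 indicate, and that SAP 6.3.1 contains no on-treatment restriction.

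The protocol point holds as an inconsistency of wording. Sections 6.4.2 and 6.11 conflict on when the study ends. Section 5.4 gives no period for its prohibition and no cross-reference to 6.5.1 and 6.9.1. No passage states the antiretroviral arrangement for completers between the two visits. That silence needs clearing up; it is not evidence of a planned treatment interruption.

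**What to change.** **SAP 6.3.2.6.** Add one sentence restricting the by-visit HIV-1 RNA analyses to on-HIV-treatment data as Section 6 already defines it (last dose of HIV study drug plus 1 day). List the 30-Day Follow-Up HIV-1 RNA separately, labelled as off study drug.

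The alternative is to bound Week 32 so that the 30-Day visit is excluded. This is better done by visit than by a fixed study day: with a 4-week delay the scheduled sample can fall on Day 248–256, inside the Day 244–264 range of follow-up samples from undelayed subjects, so no single cut-off day separates the two.

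The cost is slightly fewer records at Week 32. Under the on-treatment restriction, subjects who stopped HIV study drug early but stayed in follow-up would count as missing at later visits: failures under M=F, excluded under M=E. If the sponsor wants their later values kept, excluding only the 30-Day visit does that.

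**Protocol 5.4, 6.4.2, 6.5.1, 6.9.1, 6.11 and 6.12.** Reconcile these in an amendment or site letter: one definition of end of study, a stated period for the 5.4 prohibition, and cross-references to the replacement-regimen provisions. The clinical content is for the sponsor. This takes a few sentences and no new visit, sample or subject.
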